## 4.2. Exclusion Criteria

Any potential subject who meets any of the following criteria will be excluded from participating in the study:

#### Diabetes-Related/Metabolic

- 1. History of DKA, T1DM, pancreas or β-cell transplantation, or diabetes secondary to pancreatitis or pancreatectomy or maturity-onset diabetes of the young (MODY). See Attachment 8, Maturity-Onset Diabetes of the Young (MODY).
- 2. On any AHAs other than metformin, or injectable insulin within 8 weeks of the first dose of study drug (ie, Day 1).
- 3. Repeated (ie, 2 or more over a 1-week period) fasting SMBG glucose measurements >270 mg/dL (>15 mmol/L) during the pretreatment phase, despite reinforcement of diet and exercise counseling.

**Note:** Subjects with fingerstick glucose >270 mg/dL (>15 mmol/L) may have their AHA regimen adjusted and be rescreened once on a stable regimen for at least 8 weeks.

- 4. Severe hypoglycemia (defined as an event for which the subject required assistance from another person, or which resulted in seizure or loss of consciousness) within 6 months prior to Day 1. (See Attachment 4, Hypoglycemia: Definition, Symptoms and Treatment).
- 5. History of hereditary glucose-galactose malabsorption or primary renal glucosuria.

## Renal/Cardiovascular

6. Renal disease that required treatment with immunosuppressive therapy or a history of dialysis or renal transplant.

**Note:** Subjects with a history of treated renal disease, without sequelae, may participate.

49

## Gastrointestinal

7. Known significant liver disease (eg, acute hepatitis, chronic active hepatitis, cirrhosis).

## Laboratory

8. Persistent elevation in capillary blood ketones ≥0.6 mmol/L in the absence of concomitant illness or other identified precipitating factor during the screening period. Persistent elevation is defined as capillary blood ketone values ≥0.6 mmol/L obtained on ≥2 consecutive days.

**Note:** Subjects with capillary ketone levels  $\geq 0.6$  mmol/L in the presence of precipitating factors (eg, acute illness, non-compliance with insulin treatment) may have the screening or run-in period extended by up to 2 weeks if it is the investigator's opinion that precipitating factor/concomitant illness will be resolved and the subject will no longer meet the exclusion criterion. If, following resolution of the precipitating factor(s), the repeat assessment of capillary blood ketones shows values  $\geq 0.6$  mmol/L, the subject must be excluded.

**Note:** To avoid the confounding effect of overnight fasting on ketogenesis, for the pre-specified ketone assessment procedures, the blood ketone measurements should be obtained in a non-fasting state. If non-symptomatic ketone elevations are found in the fasting state, subjects should be instructed to repeat the ketone measurement after breakfast.

9. eGFR is <60 mL/min/1.73m^2 as assessed by Schwartz formula (see Attachment 7, Clinical Laboratory Tests).

**Note**: A one-time repeat measurement is allowed, at the discretion of the investigator, if the value for eGFR is not consistent with prior values.

10. Alanine aminotransferase level >5.0 times the upper limit of normal (ULN) or total bilirubin >1.5 times the ULN at screening (for elevations in bilirubin: if, in the opinion of the investigator and agreed upon by the sponsor's medical officer, the elevation in bilirubin is consistent with Gilbert's disease, the subject may participate).

### **Other Conditions**

11. History of malignancy within 5 years before screening (eg, any evidence of active disease within 5 years, or diagnosis of malignancy within this period).

**Note**: Subjects with squamous or basal cell carcinomas of the skin, carcinomas in situ of the cervix, or a malignancy that in the opinion of the investigator, with concurrence with the sponsor's medical monitor, is considered cured with minimal risk of recurrence, may participate.

12. Major surgery (ie, requiring general anesthesia) within 12 weeks before screening, or has not fully recovered from surgery, or planned surgery during the participation of the current study.

**Note:** Subjects with planned surgical procedures to be conducted under local anesthesia may participate.

13. History of non-traumatic amputation within past 12 months of screening, or an active skin ulcer, osteomyelitis, gangrene, or critical ischemia of the lower extremity within 6 months of screening.

# Medications/Therapies

- 14. Previously been or is currently being treated with an SGLT2 inhibitor, or the subject has participated, or is currently participating in a canagliflozin study.
- 15. Known allergies, hypersensitivity, or intolerance to canagliflozin or its excipients (refer to the Investigator's Brochure).
- 16. Current use of corticosteroid medication or immunosuppressive agent, or likely to require treatment with a corticosteroid medication (for longer than 2 weeks in duration) or an immunosuppressive agent.
  - **Note:** Subjects using inhaled, intranasal, intra-articular, or topical corticosteroids, or corticosteroids in therapeutic replacement doses may participate.
- 17. Current use of anticonvulsant medication or is likely to require treatment with anticonvulsant medication.
- 18. Received an active investigational drug (including vaccines) or used an investigational medical device within 12 weeks before the planned start of treatment.

### General

- 19. History of drug or alcohol abuse within 3 years before screening.
- 20. Pregnant or breast-feeding or planning to become pregnant during the study.
- 21. Child or adolescent of an employee at the investigational study center, whose parent/legally accepted representative has direct involvement in the proposed study or other studies under the direction of that investigator or study center.
- 22. Any condition that in the opinion of the investigator or sponsor's medical monitor would make participation not in the best interest of the subject or could prevent, limit, or confound the protocol-specified assessments.

Investigators should ensure that all study enrollment criteria have been met and determine that the subject has not had any interval change in clinical status since screening. Before randomization, subjects whose status changes after screening, such that they now meet an exclusion criterion, should be excluded from participation. Section 17.4, Source Documentation, describes the required documentation to support meeting the enrollment criteria.

#### 4.3. Prohibitions and Restrictions

Potential subjects must be willing and able to adhere to the following prohibitions and restrictions during the course of the study to be eligible for participation:

• Female subjects of childbearing potential who are heterosexually active, must remain on a highly effective method of birth control throughout their participation in the study and for at least 30 days after the last dose of study drug (refer to Section 4.1, Inclusion Criteria and refer to Section 12.2.3, Pregnancy, for instructions in cases of a positive pregnancy test).

- Prohibited medications include other SGLT2 inhibitors, or other AHAs that are not approved
  for use in pediatric population (including commercially available canagliflozin). Subjects
  must not take any other investigational agents during the study (if a subject prematurely
  discontinues the study drug but continues to participate in the post-treatment follow-up
  phase, entering another investigational study is discouraged but is not prohibited; however,
  entering another canagliflozin study is prohibited).
- Subjects should not collect first morning void urine specimens during acute illness with fever. The collection and respective visit should be postponed until the subject is recovered from the acute illness.
- Exceptionally strenuous exercise may affect urine protein excretion and other safety laboratory results; for this reason, strenuous exercise should be avoided within 72 hours before planned study visits.

# 4.4. Repeat Testing and Subject Rescreening

During the screening period and prior to initiation of the single-blind placebo run-in period at Week -2, a non-qualifying laboratory test value may be repeated one time, at the discretion of the investigator and where there is a clinical reason to do so. In subjects for whom a one-time repeat measure is deemed clinically appropriate, the repeat measure should be assessed within the screening period and prior to recording the subject as having failed screening.

Subjects who do not satisfy entry criteria based on a physical or laboratory measurement either during the initial screening assessment or following an allowable one-time repeat assessment will be reported as having failed screening and may be rescreened once, at the discretion of the investigator and with concurrence of the sponsor's medical monitor. Additional rescreening may be discussed with the sponsor's medical monitor to evaluate eligibility into the study on a case by case basis. Rescreening will typically require that all screening parameters be repeated, including the signing of a new ICF and the completion of a full screening visit with a comprehensive central laboratory review. Rescreened subjects must meet all entry criteria to be considered eligible for the study.

## 5. TREATMENT ALLOCATION

#### Stratification

Dynamic randomization (ie, covariate-adjusted randomization) will be used in an effort to maintain balance between treatment groups with respect to the following stratification factors: AHA background (ie, diet and exercise only; metformin monotherapy; insulin monotherapy or combination of metformin and insulin) and age group ( $\geq 10$  to < 15 years old;  $\geq 15$  to < 18 years old). The stratification process will be handled after logging on to the IWRS being used for the study.

## **Randomization and Blinding Procedures**

In dynamic randomization, a new subject is sequentially assigned to a particular treatment group by taking into account the specific covariates and previous assignments of subjects. This approach uses the method of minimization by assessing the imbalance of sample size among the

covariates listed above. Subjects will be randomized to 1 of 2 treatment groups based on a computer-generated dynamic randomization algorithm prepared by or under the supervision of the sponsor before the study. This approach seeks to maintain balance between treatment groups with respect to the AHA background and age group. The goal is to have at least 30% of participants that will be  $\geq 10$  to < 15 years of age, 30% to < 65% of participants that will be female in each age group ( $\geq 10$  to < 15 years and  $\geq 15$  to < 18 years), and 30% of participants that will have ethnicity and lifestyle comparable to Europe.

Based on this approach, the study drug will be packaged and labeled. Medication numbers will be preprinted on the study drug labels and assigned as subjects qualify for the study and are assigned to double-blind treatment. At baseline (Day 1), the randomization number, medication numbers, and the treatment code, which is linked to the dynamically-generated randomization schedule, will be assigned after logging on to the IWRS designated by the sponsor. The requestor must use his/her own user identification (ID) and personal identification number (PIN) when accessing the IWRS and will then enter the relevant subject details to uniquely identify the subject. Based on this information, the IWRS will assign a unique treatment code, which will dictate the treatment assignment and matching study drug kit for the subject. As subjects are randomized to treatment, the IWRS will assign a study drug kit to be dispensed at that visit. New study drug kits will be assigned each time the IWRS is assessed for dispensing additional study drug.

At the baseline (Day 1) visit, all eligible subjects, regardless of the treatment assignment to canagliflozin 100 mg will be assigned canagliflozin 100 mg kits and matching placebo kits.

The dynamically-generated randomization code that links the randomization number assigned to the subject with a treatment group assignment will be maintained within the IWRS. This randomization code will not be provided to the investigator unless required, as described below, for unblinding in emergency situations.

Under normal circumstances, the blind should not be broken until all subjects have completed the study and the database is finalized. However, the treatment blind may be broken to provide unblinded information to the study site only if specific emergency treatment/course of action would be dictated by knowing the treatment status of the subject. In such cases, the investigator may in an emergency determine the identity of the treatment by assessing the IWRS. It is recommended that the investigator contact the sponsor or its designee if possible to discuss the particular situation before breaking the blind. The reason for unblinding is not captured through the IWRS. Telephone contact with the sponsor or its designee will be available 24 hours per day, 7 days per week. In the event the blind is broken, the sponsor must be informed as soon as possible. The date and reason for the unblinding must be documented in the appropriate section of the eCRF, and in the source document. The documentation received from the IWRS indicating the code break must be retained with the subject's source documents in a secure manner (eg, sealed envelope) so as not to unblind the treatment assignment to the study site or sponsor personnel. The investigator is also advised not to reveal the study treatment assignment to the study site (except as necessary for the clinical management of the subject) or sponsor personnel.

In general, randomization codes will be disclosed fully only if the study is completed and the clinical database is closed. The translation of randomization codes into treatment and control groups will be disclosed only to those authorized.

To avoid the potential unblinding after randomization (Day 1), FPG values will be masked to the study sites and to sponsor. Similarly, HbA1c values will be masked, except for (1) Day 1 value, (2) Week 12 value, and (3) after glycemic rescue therapy has been initiated.

In addition, unless required by urgent subject management, investigators should obtain all post-baseline urinalyses through the central laboratory and not by a local laboratory so as to avoid potential for unblinding related to urine glucose results (which will not be reported by the central laboratory). Investigators will be counseled to avoid performing local urinalysis with dipstick. If a urinalysis must be performed locally for appropriate subject management (eg, to evaluate a potential infection), investigators should request microscopic rather than dipstick urinalysis (if microscopic evaluation is considered clinically sufficient).

#### 6. DOSAGE AND ADMINISTRATION

# 6.1. Blinded Study Drug

# 6.1.1. Single-Blind Placebo Study Drug

Upon completion of initial screening, all eligible subjects will receive 1 placebo tablet (1 placebo tablet matching canagliflozin 100 mg) prior to the first meal of the day for a total of 2-weeks to assess compliance.

Subjects will take the last dose of single-blind placebo study drug on the day prior to the baseline (Day 1) visit. The investigational site staff should avoid disclosing to the subject that the 2-week single-blind placebo run-in period drug is placebo.

# 6.1.2. Double-Blind Study Drug

On Day 1, subjects will be randomly assigned in a 1:1 ratio to 1 of 2 treatment groups: canagliflozin 100 mg, or matching placebo.

On Day 1, the first dose of double-blind study drug will be administered at the study site after all baseline procedures have been completed.

After Day 1, subjects will be counseled to take their dose of canagliflozin 100 mg or matching placebo, once daily, before the first meal of the day.

At Week 13, subjects who have a Week 12 HbA1c of  $\geq$ 7.0% and eGFR  $\geq$ 60 mL/min/1.73m^2 will be re-randomized to either remain on double-blind canagliflozin 100 mg (or matching placebo) or to up-titrate to double-blind canagliflozin 300 mg (or matching placebo). A double-dummy approach will be used to maintain the blind to dose-assignments as indicated below:

- Subjects initially randomized to placebo and undergoing re-randomization at Week 13, will continue receiving 1 tablet of placebo matching canagliflozin 100 mg and will **ADD** 1 tablet of placebo matching canagliflozin 300 mg for the remainder of the double-blind treatment period.
- Subjects initially randomized to canagliflozin 100 mg and re-randomized to remain on canagliflozin 100 mg at Week 13, will continue receiving 1 tablet of canagliflozin 100 mg and will **ADD** 1 tablet of placebo matching canagliflozin 300 mg for the remainder of the double-blind treatment period.
- Subjects initially randomized to canagliflozin 100 mg and re-randomized to up-titrate to canagliflozin 300 mg at Week 13, will switch to 1 tablet of placebo matching canagliflozin 100 mg and will ADD 1 tablet of canagliflozin 300 mg for the remainder of the double-blind treatment period.

Subjects **not** undergoing re-randomization (ie,  $HbA_{1c}$  of <7.0% or eGFR <60 mL/min/1.73m^2) at Week 13 will continue to receive 1 tablet of canagliflozin 100 mg or 1 tablet of placebo matching canagliflozin 100 mg for the remainder of the double-blind treatment period.

A summary of study drug administration is provided in Table 1.

Table 1: Summary of Dose Level and Number of Tablets by Study Period and Treatment

Study Period	Criteria for re-randomization	Treatment Group: canagliflozin	Treatment Group: placebo
Day 1 to re- randomization	Not applicable	1 tablet of canagliflozin 100 mg	1 tablet of placebo matching canagliflozin 100 mg
Re- randomization to Week 52	NOT eligible for re- randomization if:  HbA 1c <7.0% or eGFR <60 mL/min/1.73m 	1 tablet of canagliflozin 100 mg	1 tablet of placebo matching canagliflozin 100 mg
Re- randomization to Week 52	Eligible for re-randomization if:  • HbA 1c $\geq$ 7.0% and eGFR $\geq$ 60 mL/min/1.73m 	1 tablet of canagliflozin 100 mg  AND 1 tablet of placebo matching canagliflozin 300 mg  or 1 tablet of canagliflozin 300 mg  AND 1 tablet of placebo matching canagliflozin 100 mg	1 tablet of placebo matching canagliflozin 100 mg  AND  1 tablet of placebo matching canagliflozin 300 mg

The study drug must be swallowed whole with liquid and not chewed, divided, dissolved, or crushed. If the subject does not take the study drug within 12 hours after the first meal of the day, the dose of study drug should be skipped for that day and the subject should be instructed to take the study drug on the following day before the first meal of the day.

Study drug treatment may be interrupted (eg, for safety and/or tolerability reasons such as hospitalizations for major surgical procedure or serious medical illness). In addition, study drug treatment should be interrupted in clinical situations known to predispose to ketoacidosis

(eg, prolonged fasting due to acute illness or surgery [see Section 9.2.2, Management of Blinded Study Drug During Ketonemia]).

For subjects who develop conditions that are associated with amputations, such as a lower-extremity infection, skin ulcer, osteomyelitis, gangrene, or critical limb ischemia, study drug should be interrupted until the condition has resolved in the opinion of the investigator. In the event of an amputation, restarting of dosing with canagliflozin should only be done after careful consideration of the individual risk:benefit and following discussion with the sponsor.

Study drug treatment interruption, occurring for any reason, will be documented on the eCRF. Study drug should be reinstituted once the subject has recovered and the safety and/or tolerability concern is no longer present.

Study-site personnel will instruct subjects on how to store study drug for at-home use as indicated for this protocol.

On the days of study visits when fasting blood samples are collected (refer to the Time and Events Schedule that follows the synopsis), subjects will be instructed to refrain from taking the study drug before the clinic visit. The subject will be instructed to take the dose of study drug before the subject's next meal.

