# 9.2.1.2. Ketone Measurements During Periods of Increased Risk of Ketonemia

It is paramount that subjects and parents/legal guardians are educated on obtaining ketone measurements whenever they experience potential causes of ketone elevation that might lead to ketoacidosis if not identified and treated in time.

These possible precipitating factors include, but are not limited to:

- Acute illness
- Significant and/or sudden reduction in insulin dose (eg, non-compliance with insulin treatment regimen)
- Prolonged fasting or low carbohydrate diet
- Dehydration and/or a marked increase in physical activity
- Increased alcohol consumption
- Undergoing a minor procedure (eg, dental extraction)
- Significant physiologic stress

Subjects and parents/legal guardians will be instructed to test their ketone levels in the presence of these possible precipitants, regardless of the presence of symptoms of DKA (such as nausea, abdominal pain, dehydration, polyuria), as these are nonspecific and might be interpreted as gastroenteritis, or signs and symptoms of osmotic-diuresis related to the use of study drug. In addition, it is paramount to instruct subjects and parents/legal guardians to test ketones in such occasions regardless of the concomitant glucose level, as blood glucose might be incongruously low (<250 mg/dL [<13.9 mmol/L]) and not as high as one would expect to observe during ketosis and DKA.

Ketone measurements performed during illness or periods of increased risk of ketone elevation, should preferably be done *prior* to dosing of study drug to allow prompt interruption of study drug, if required.

During sick days, subjects must refer to the algorithm (see Attachment 2, Suggested Algorithm for Ketone Monitoring and Findings of Elevated Ketones) to determine, based on severity of illness, degree of ketosis, and ability to increase insulin dose and food intake, the appropriate frequency of retesting of ketones and glucose, action with blinded study drug, need to seek immediate medical attention, or to contact the study site.

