# 9.2.2. Management of Blinded Study Drug During Ketonemia

Subjects will be instructed to interrupt blinded study drug for the following reasons:

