# Surgery and invasive procedures

- Subjects undergoing pre-planned major surgery (eg, requiring general anesthesia), will be instructed to interrupt blinded study drug at least 3 days prior to the surgery. Study drug may be resumed after recovery from surgery and after consultation with the investigational site.
- Subjects undergoing minor surgical and non-surgical procedures will be instructed to interrupt study drug on the day of the procedure (or starting the day prior to the procedure if deemed appropriate, such as in preparation for a colonoscopy) and resume dosing on the following day if their non-fasting blood ketone level on the day following the procedure is <0.6 mmol/L and the subject has completely recovered from the procedure.

- Persistent elevated ketonemia ≥0.6 mmol/L (with or without symptoms of ketosis, regardless of concomitant glucose levels)
  - Persistent elevated ketonemia is defined as blood ketone levels ≥0.6 mmol/L and confirmed by a repeat assessment (eg, within 1 hour or sooner, if in the presence of symptoms). If urine ketone is being used to assess ketone status, then a value of "moderate/large" urine ketone will be used.

- In the presence of illness/symptoms, or presence of potential risk factors for ketosis (eg, insulin dose reduction, etc), subjects should assess ketone levels *prior* to dosing blinded study drug to allow timely interruption of study drug should ketone levels be elevated.

Subjects should be advised to contact the study site immediately for further instructions regarding management of blinded study drug, insulin dose-adjustment, and possible need to seek immediate medical attention.

Cause of dose interruption of blinded study drug and duration of study drug interruption will be captured on a specific adverse event eCRF and study drug administration eCRF, respectively.

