#### Generally,

- thirst, frequent urination, and sweet breath may occur with blood ketones <1.0 mmol/L (small/moderate urine ketones),
- dry mouth, nausea, stomach cramps, and/or vomiting may occur with blood ketones from 1.0 to 3.0 mmol/L (moderate/large urine ketones),
- labored deep breathing, extreme weakness, confusion, and eventually unconsciousness (coma) may occur with blood ketones >3.0 mmol/L (large urine ketones)

The study site personnel must also educate the subject on the importance of measuring capillary blood ketone (or urine ketones) regardless of the concomitant glucose levels, as these may be not as elevated (ie, >250 mg/dL [>13.9 mmol/L]) as usually observed during DKA.

Also, the subject must be instructed when to call the study site and what action to take while awaiting further instructions and when to seek immediate medical attention. In particular, in the presence of blood ketones ≥0.6 mmol/L (repeated and confirmed), subjects are required to:

- contact the study site to receive further instructions based on the clinical assessment of the investigator or delegate
- interrupt study drug

- increase insulin if subject is on insulin (without increasing risk of hypoglycemia)
- increase carbohydrate and fluid intake
- seek immediate medical attention if appropriate increases in insulin and fluid intake cannot be managed by the subject (due to hypoglycemia, vomiting etc) and/or the subject shows signs/symptoms of DKA such as nausea, vomiting, abdominal pain, dehydration, or rapid breathing

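### The sick-day instructions given to families omit the preventive stop that Protocol 6.1.2 calls for when acute illness leads to prolonged fasting

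*Protocol*

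**What the plan says.** Protocol 6.1.2 first permits interruption for safety or tolerability reasons, including serious illness. It then adds a firmer rule aimed at ketoacidosis: "In addition, study drug treatment should be interrupted in clinical situations known to predispose to ketoacidosis". The example, with its cross-reference, is "prolonged fasting due to acute illness or surgery [see Section 9.2.2, Management of Blinded Study Drug During Ketonemia". No ketone level is attached.

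Protocol 9.2.2, the section cited, opens with "Subjects will be instructed to interrupt blinded study drug for the following reasons". Two reasons follow.

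- **Surgery and invasive procedures.** Study drug stops at least 3 days before planned major surgery and on the day of a minor procedure (or the day before where appropriate). Neither stop depends on ketones. After a minor procedure, dosing resumes the next day "if their non-fasting blood ketone level on the day following the procedure is <0.6 mmol/L" and the subject has fully recovered.
- **Persistent ketonemia.** "Persistent elevated ketonemia is defined as blood ketone levels ≥0.6 mmol/L and confirmed by a repeat assessment". If urine is tested instead, the trigger is a moderate or large result. A bullet on illness and risk factors asks for ketones to be measured before dosing "to allow timely interruption of study drug should ketone levels be elevated".

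Protocol 9.2.1.2 lists acute illness and prolonged fasting among the reasons to test ketones. For sick days it sends subjects to Attachment 2 to settle the "appropriate frequency of retesting of ketones and glucose, action with blinded study drug".

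Attachment 1 tells subjects to interrupt study drug under this condition: "in the presence of blood ketones ≥0.6 mmol/L (repeated and confirmed), subjects are required to". Attachment 2 places its skip-the-dose step under the same confirmed threshold.

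**The concern.** For illness, the protocol holds two rules that act at different times. Section 6.1.2 is preventive: stop because the child is ill and has been fasting for a prolonged period. Section 9.2.2 and the attachments are reactive: stop once a ketone rise has been confirmed. The family at home works from the reactive text.

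The protocol's own rationale makes the difference relevant. Section 3.2 explains that acute illness raises insulin resistance and lowers the functional insulin-to-glucagon ratio. It adds that ketoacidosis on this drug may appear at lower glucose than expected and be recognised late. Section 1.1.1 reports mean half-lives of 11.3 to 15.2 hours in pediatric subjects, so a dose taken before ketones rise is still partly present afterwards. Diabetic ketoacidosis is an adverse event of special interest with 24-hour reporting (Section 12), and a serious, biochemically confirmed case ends study drug (10.2.1). What is at stake is a safety instruction, not an efficacy result.

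**Working it through.** No arithmetic applies beyond a count of instructions. The check takes one case through each text: acute illness, prolonged fasting, blood ketones below 0.6 mmol/L (or urine ketones below moderate).

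| Protocol text | What it says for this case |
|---|---|
| 6.1.2 | Interrupt; no ketone condition |
| 9.2.2, procedures | Does not apply |
| 9.2.2, persistent ketonemia | Not met; test before dosing |
| 9.2.1.2 | Test ketones; follow Attachment 2 |
| Attachment 1 | Stop instruction not triggered |
| Attachment 2 | Skip-dose step not triggered |
| COVID-19 appendix | Reminds families of the same sick-day instructions |

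**Count of stop instructions in 9.2.2 and Attachments 1 and 2**

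1. 9.2.2, major surgery: no ketone threshold for stopping.
2. 9.2.2, minor procedures: no ketone threshold for stopping.
3. 9.2.2, persistent ketonemia: confirmed ketones of at least 0.6 mmol/L, or moderate/large urine ketones.
4. Attachment 1: repeated and confirmed ketones of at least 0.6 mmol/L.
5. Attachment 2: confirmed ketones of at least 0.6 mmol/L, with moderate/large urine ketones as the approximate equivalent.

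That is 2 + 3 = 5 instructions, and 0 of 5 cover illness-related prolonged fasting below the threshold. Of the 2 situations in the 6.1.2 example (illness, surgery), 9.2.2 carries over 1. The count describes only these three places. It does not include 6.1.2 itself or the volume-depletion rule in 12.2.1, and it is not a measure of risk.

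**Safeguards elsewhere, and how far each reaches**

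- *Repeat testing (Attachment 2).* Ketones are measured until the illness has passed, so a later confirmed rise does lead to a stop. No retest interval is given below 0.6 mmol/L; the 4-to-6-hour schedule sits under the raised-ketone heading.
- *Site contact (end of 9.2.2).* Subjects are to call the site at once about managing study drug. This sentence follows the illness bullet and can be read as covering illness, or as covering only raised ketones.
- *Site contact (12.2.1).* Subjects call for symptoms of ketoacidosis such as nausea, vomiting, abdominal pain or unusual fatigue. This covers many ill children, but it depends on symptoms.
- *Feeding advice (Attachment 1).* Ill subjects are told to take small, frequent meals, carbohydrate every 1 to 2 hours, and fluids. This works directly against prolonged fasting. It says nothing about study drug if the child still cannot eat.
- *Volume depletion (12.2.1).* Study drug may be interrupted with no ketone condition, but this rests on an evaluation at a visit.
- *Dosing before the first meal (6.1.2).* This is a timing rule, not an instruction to hold the dose.
- *Clinical judgment (Attachment 2).* Available once the investigator knows of the illness.

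Together these narrow the case without removing it.

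**The case against.** The strongest reply is that this is silence and not conflict. Section 9.2.2 is titled for ketonemia, so a child without ketonemia is partly outside its scope. Attachment 2 is presented as a suggested algorithm and as guidance subject to judgment, so it does not displace 6.1.2. An investigator who is called can and should apply 6.1.2. The remaining case also needs several things at once: a prolonged fast despite the feeding advice, ketones staying below the threshold, and none of the symptoms that prompt a call.

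Most of that stands. A reader might infer that the protocol tells families to keep dosing below 0.6 mmol/L, or that 6.1.2 and the attachments flatly contradict each other. The documents do not support either reading: no text orders dosing to continue, and 6.1.2 remains in force. Nor does 6.1.2 cover any missed meal; its word is prolonged.

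The scope argument does not fully answer the point. Section 6.1.2 cites 9.2.2 for this very example, and 9.2.2 already reaches beyond ketonemia by handling surgery without a ketone threshold for stopping. Section 9.2.1.2 also directs families to Attachment 2 for the decision on study drug, so its silence has practical weight.

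A second reply is that consistency could be restored the other way, by tying the illness example in 6.1.2 to the 0.6 mmol/L trigger, a level that 3.2 justifies. That is open to the sponsor. It would, however, give up the preventive stop for illness while keeping it for minor procedures, and 3.2 gives illness a clear rationale as a risk.

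**Conclusion.** The point holds as a narrow omission. Section 6.1.2 calls for study drug to be interrupted during prolonged fasting from acute illness, whatever the ketone level. Section 9.2.2 carries over the surgery half of that rule, and the attachments carry over neither half as a preventive stop. For illness, all three wait for confirmed ketones of at least 0.6 mmol/L or the urine equivalent. A family following the sick-day text exactly can therefore give a dose that 6.1.2 says should be withheld.

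The remaining case is a child with a prolonged illness-related fast, ketones below the threshold, no symptoms that prompt a call, no other contact with the site, and no visit at which volume depletion is found. Its frequency is not given in the documents, and no risk estimate is made. The instructions go to at least 146 subjects, of whom at least 73 are assigned to canagliflozin. If the site-contact sentence closing 9.2.2 is meant to cover illness without raised ketones, the gap is smaller still, but the families' instructions should then say so.

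No effect on the primary analysis is claimed.

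**What to change.** Add one reason for interruption to 9.2.2 and to Attachments 1 and 2: prolonged fasting caused by acute illness, whatever the ketone level. Attach two instructions to it:

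- contact the site;
- resume once the child has recovered, is eating, and has a non-fasting blood ketone level below 0.6 mmol/L.

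This matches the rule 9.2.2 already applies to minor procedures: stop without a ketone condition, restart on recovery with ketones below the threshold. Keep the qualifier prolonged, so that the change aligns the texts without widening 6.1.2.

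The cost is one added reason in three places and reissued subject instructions. There would be some extra short interruptions of study drug, expected to be few, though the documents give no frequency from which to estimate the number. The eCRF already records interruptions, so no new procedure or data item is needed.
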